## Transcranial Direct Current Stimulation to Lower Neuropathic Pain in People With Multiple Sclerosis

Purpose

The purpose of this study is to investigate the effects of different intensities of transcranial direct current stimulation (tDCS) on neuropathic pain and fatigue in people with MS. We will conduct three different tDCS conditions (sham, 2 mA, and 4 mA) on 5 consecutive days each. We will evaluate pain and fatigue with specific questionnaires and measure fatigability with an isokinetic device.

Our research question is whether tDCS can lessen neuropathic pain and increase fatigue resistance in people with MS and if a higher intensity stimulation (4 mA) provides additional pain and fatigue improvements. We hypothesize less neuropathic pain and increased fatigue resistance after either of the tDCS sessions and that the 4 mA condition will better improve pain and fatigue compared with the 2 mA condition.

Significance and Background

People with Multiple Sclerosis (PwMS) are at an over five-fold increased risk of receiving treatment for neuropathic pain. This pain type appears to be the primary factor behind the overall increased risk of pain treatment for PwMS. However, the management of neuropathic pain syndromes is currently a challenging task because only 40% to 60% of patients experience a favorable outcome from pharmacological treatments. Several studies have shown that most of the currently available treatments, including antidepressants, opioids, and topical anesthetics, have limited long-term effectiveness and are often associated with moderate or even severe adverse effects. It is generally agreed that improved therapies are needed for addressing symptoms of MS such as neuropathic pain. Furthermore, to fight the opioid epidemic in the US, safer treatments are urgently needed.

tDCS has significantly advanced in the past 15 years as a treatment tool and has been successfully used by the PI. It has a theoretical advantage when compared with traditional neuropathic pain treatments because it directly affects central neural targets, thus having a potentially stronger effect on central sensitization. On the other hand, its effects may take longer to appear (i.e., only after 5–10 sessions, subjects may notice pain decrease). Because of its relatively low cost, ease of use, and safety profile, tDCS may be a suitable alternative treatment of pain in various disorders.

Several preliminary studies have demonstrated initial efficacy of tDCS for pain control. Our own preliminary case study on one PwMS, who was resistant to pain medication, using the same tDCS protocol proposed here (2 mA condition), showed reduced pain ratings (VAS, NPSI) after the 5 consecutive days. Additionally, because pain and fatigue are strongly correlated, we will investigate the effects of tDCS on fatigability in PwMS at the same time. Furthermore, because there is a potential to increase the benefits of tDCS by increasing stimulation intensity, a comparison of different intensities (2 mA and 4 mA) will also be conducted.

Methods

Prospective participants, men and women with MS, will be recruited. To accomplish this study, 20 participants will need to complete 3 randomly ordered blocks of protocols (sham, 2 mA, 4 mA), separated by at least one week. Each block involves 5 daily sessions at the INPL. The duration of each session will be approximately one hour and will be completed at the same time of day for each subject. We expect data collection to last 6 months. Each session will be a combination of questionnaires, leg strength assessment, and an isokinetic fatigue test.

Leg strength assessment: Isokinetic (concentric/concentric) flexion and extension of the knee at 60°/s will be performed five times to determine the more-MS affected leg. When strength difference between the left and right legs is less than 10%, the more affected side will be based on the participant's self-report.

Isokinetic fatigue test: Participant's will perform 40 consecutive repetitions of isokinetic concentric/concentric

flexion and extension of the knee on the more-affected leg at 120 degree/sec.

In the initial session (i.e., Block 1, Session 1) subjects will 1) be consented, 2) complete the Patient Determined Disease Steps (PDDS) questionnaire, 3) the Fatigue Severity Scale (FSS), 4) Neuropathic Pain Questionnaire (NPQ), 5) Visual analog scale (VAS), 6) perform a leg strength assessment, 7) perform an isokinetic fatigue test, and 8) undergo either sham tDCS, tDCS at 2 mA, or tDCS at 4 mA, depending on the randomized block.

tDCS treatment protocol: A tDCS device (Soterix) will deliver a small direct current through two sponge surface electrodes (5cm x 5cm, soaked with 15 mM NaCL). The positive electrode will be placed over the motor cortex representation of the more affected leg, and a second electrode will be placed on the forehead above the contralateral orbit. The three protocols blocks (sham, 2 mA, 4 mA) will be performed in randomized order.

tDCS Block: The participant will receive tDCS for 20 min at an intensity of 2 mA or 4 mA while seated comfortably and quietly in a room. The intensity will start at 0 mA and will be incrementally increased to 2mA or 4 mA over the initial 30 seconds. At the 19:30 minute time point, the current will gradually be reduced from 2 mA (or 4 mA) to 0 mA.

Sham block: Identical to the tDCS block, except the participants will only receive the initial 30 seconds of ramp-up, after which the current will be set to 0 for the remainder of the 20 minutes.

The remaining sessions of first block (i.e. Block 1, Sessions 2-5) will be as follows: In Sessions 2 and 4, the subjects get the tDCS or sham treatment, after which they will complete the fatigue and pain questionnaires (FSS and NPQ). Sessions 3 will be the same as Sessions 2 and 4, except that the isokinetic fatigue test will be performed at the beginning (i.e., before the tDCS or sham treatment). Session 5 will start with tDCS or sham treatment, then the isokinetic fatigue test, and finally the fatigue and pain questionnaires.

Blocks 2 and 3 will be completed in the same manner as Block 1, except that the subjects will not redo the PDDS, VAS, and BDI in Session 1 and the treatment will shift to either tDCS at 2 mA, tDCS at 4 mA, or sham, depending on how the blocks were randomized. Block 2 will be randomly assigned based on uncompleted stimulation blocks.

**Inclusion Criteria:** medically diagnosed with Multiple Sclerosis, 18-70 yrs. of age, moderate disability (Patient Determined Disease Steps (PDDS) core 2-6), self-reported differences in function between legs, able to walk for 6 min, and presenting with chronic, drug-resistant, neuropathic pain. Chronic neuropathic pain will be defined as a constant or intermittent sensory symptom with unpleasant feelings or pain, lasting more than 1 month and having a stereotyped neurological distribution and superficial localization. To differentiate neuropathic from spasticity-associated pain, patients need to score greater than 0 on the Neuropathic Pain Questionnaire (NPQ) to qualify for the study. A minimum score of 40 (0 = no pain, 100 = worst possible pain) on the visual analog scale (VAS) for pain perception at baseline will be required to be enrolled in the study. All analgesic medications will be discontinued at least 24 hours before entering the study and not be used until study participation is completed.

**Exclusion Criteria:** relapse within last 60 days, high risk for cardiovascular disease (ACSM risk classification), changes in disease modifying medications within last 45 days, concurrent neurological/neuromuscular disease, hospitalization within last 90 days, diagnosed depression, and inability to understand/sign informed consent.

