Physiological studies have also assessed the safety of tDCS when applied within the aforementioned stimulation guidelines. For example, there was no neuronal damage as measured by serum neuron-specific enolase (Stagg & Nitsche, 2011) or MRI measures of edema using contrast enhanced and diffusion-weighted MRI measures following administration of tDCS (Nitsche et al. 2004). Furthermore, tDCS did not negatively alter measures of neuropsychological function and EEG activity (Iver et al. 2005). Accordingly, rat studies using tDCS models emulating tDCS applied to humans (Liebetanz et al. 2009) showed that the current density needed to induce tissue damage or lesions was about  $1429 \text{ mA/cm}^2$ , whereas the current densities used in human studies are between  $0.04$  and  $0.08 \text{ mA/cm}^2$  and in this proposal are  $0.029 \text{ mA/cm}^2$  and  $0.11 \text{ mA/cm}^2$ . Lastly, safety and tolerability results from two of our recent studies currently under review for publication provide evidence that 4 mA tDCS is safe and well-tolerated, with most sensations and sensation severities similar to sham and 2 mA tDCS. In conclusion, the tDCS stimulation parameters in this study are identical to the most common in the literature and have been proven to be exceptionally safe and well-tolerated.

The probability is very unlikely that harm may occur (see above). Based on the available literature a slight headache should be the worst possible negative effect and should be very rare. In this case, non-prescription medication should relieve the headache within 1-2 hours.

PwMS in general have a higher fall risk.

There are no emotional or psychological, financial, legal or social risks.

This was a case report: No statistical analysis.

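### The stated rule for condition order leaves balance over the six orders to chance; for 20 people an order-balanced, concealed list would avoid nearly all of a modest loss of precision

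*Protocol*

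**What the plan says.** The Methods section of the protocol sets the size and design: "20 participants will need to complete 3 randomly ordered blocks of protocols (sham, 2 mA, 4 mA), separated by at least one week". The paragraph on the tDCS treatment protocol adds "The three protocols blocks (sham, 2 mA, 4 mA) will be performed in randomized order". The paragraph on Blocks 2 and 3 gives the one operational rule: "Block 2 will be randomly assigned based on uncompleted stimulation blocks". Read as written, the second condition is drawn from the two that remain and the third follows by elimination.

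The sentence just before that rule says that treatment shifts "depending on how the blocks were randomized", which could also describe an order fixed in advance.

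The protocol mentions no randomization list, Latin square, restricted randomization or target number per order. Its word block means a five-day treatment period, so it should not be taken as evidence of blocked randomization. The document closes, at the end of Risks for subjects, with "This was a case report: No statistical analysis".

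**The concern.** In a crossover, each condition should fall about equally often in each period, so that a change over time common to all participants is not mixed with the condition effect. With three conditions there are six orders, and 20 people give an expected 3.33 per order. Independent draws at that size often leave the orders uneven.

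The consequence depends on the analysis. With a period term, unevenness makes condition and period partly collinear and widens the standard error. Without one, the nominal variance is unchanged, but any drift across blocks enters the condition comparison in proportion to the unevenness. The comparisons affected include 4 mA against 2 mA, which is a stated hypothesis.

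A period term added in a later analysis plan removes the drift but cannot restore the balance. That is settled when participants are allocated.

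**Working it through.** The protocol gives no balance, power or precision figure, so there is nothing of its own to reproduce.

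**Inputs**
- n = 20 completers, and three conditions in three periods (Purpose and Methods).
- Probability of each order: 1/3 × 1/2 = 1/6. This assumes equal, independent draws; the protocol gives no probabilities. An unrestricted order fixed in advance also gives 1/6, so both readings of the text lead to the same figures.
- Analysis: participant, period and condition effects. This is an assumption.

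**Formula.** Let M be the 3 × 3 table of how many participants receive condition k in period t. Every participant receives every condition once, so the information on the conditions, adjusted for participant and period, is C = nI − MMᵀ/n. Under perfect balance every cell of M is n/3, and a two-condition contrast has variance 2/n = 2/20 = 0.100 (in units of the within-participant variance). Results below are ratios to 0.100.

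**Two cases by hand**
1. *Balanced list of 20: three per order plus two extras, ABC and ACB.* The rows of M are A (8, 6, 6), B (6, 7, 7), C (6, 7, 7).
   - The A and B part of the information matrix is [13.2, −6.6; −6.6, 13.3].
   - Its determinant is 175.56 − 43.56 = 132.0.
   - Var(A − C) = 13.3/132.0 = 0.1008, a ratio of 1.0076. This is the worst case for such a list.
2. *An uneven draw.* The rows of M are A (12, 4, 4), B (5, 7, 8), C (3, 9, 8).
   - The A and B part is [11.2, −6.0; −6.0, 13.1].
   - Its determinant is 146.72 − 36.00 = 110.72.
   - Var(A − C) = 13.1/110.72 = 0.1183, a ratio of 1.183.

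**All allocations.** Exact enumeration of the 53,130 ways to spread 20 people over six orders, with multinomial weights, for one given contrast. Allocations where the contrast cannot be estimated have total probability of about 3 in a billion and are left out.

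| Allocation of 20 | Median | Mean | 95th percentile | Maximum | Chance above +10% |
|---|---|---|---|---|---|
| Unrestricted | +3.5% | +5.7% | +18.3% | – | 18.1% |
| Balanced list (15 cases) | – | +0.4% | – | +0.8% | 0 |

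- Standard error, unrestricted: √1.0346 = 1.017 at the median and √1.183 = 1.088 at the 95th percentile.
- Equivalent participants lost, 20 − 20/ratio: 0.67 at the median, 1.09 at the mean variance and 3.1 at the 95th percentile.
- The chance that unrestricted draws match the list's three or four per order is 1.3%.

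**Without a period term.** For a given pair of conditions, the difference in position is ±1 in four orders and ±2 in two. Its variance is (4 × 1 + 2 × 4)/6 = 2 per person, so the mean over 20 people has SD √(2/20) = 0.32 block (95th percentile of the absolute value 0.60). With the balanced list the SD is 0.09 and the maximum 0.15. A steady drift of d per block would shift the comparison by d times that difference. The protocol gives no value for d.

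**Dropout.** Suppose more people are allocated from a list in blocks of six and 20 complete at random (assumed enrolments, 60,000 simulations each). The mean excess variance is then +0.8%, +0.9% and +1.8% for 22, 24 and 30 enrolled, with 95th percentiles of +2.3%, +2.3% and +5.5%. The unrestricted figures do not change under random dropout.

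**The case against.** The strongest reply is that nothing here is wrong. Random draws from the remaining conditions are proper randomization, each order has the same chance, and choosing restricted randomization instead is a matter of efficiency. That stands: a reader might infer that the rule biases the comparison or invalidates the design, and the text supports neither.

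Second, the loss is small and conditional. At the median it is 1.7% in standard error, and there is an 82% chance that the excess variance is 10% or less. The loss of about three participants is a 95th-percentile event and should not be read as typical. The variance figures need a period term. Without one, harm depends on a drift whose size the protocol does not give, so no effect on the trial's conclusions can be shown. This also stands.

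Third, list details are often kept outside a short protocol, and a randomization document may exist. If it sets a restricted list, the figures do not apply. This limits the point but does not remove it, because the protocol does not merely stay silent: it states a rule, and following that rule as written gives no balance.

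Fourth, the closing case-report line may mean that only one person was studied. Balance over orders would then have no practical effect, so the point is about the planned 20-person design only.

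A reader might also count the 15.2% chance that some order is never used as a further harm. It is not: its cost is already in the variance figures.

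**Conclusion.** The point holds as a low-priority, cheap improvement. Following the stated rule gives avoidably lower expected precision than a balanced list, typically by a little and occasionally by a noticeable amount, and the difference cannot be recovered after allocation. It does not show bias, an invalid randomization or a contradiction in the protocol.

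The conclusion assumes equal and independent draws, 20 completers, no restricted list that the protocol leaves unmentioned and, for the variance figures, a period term in the analysis.

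**What to change.** Replace the sentence on how Block 2 is assigned with:

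> At enrolment each participant will be assigned one of the six orders of sham, 2 mA and 4 mA from a pre-generated, concealed list balanced over the six orders.

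Keep the block size in a restricted randomization document that staff who enrol or assess participants cannot see. Independent draws cannot be predicted from earlier participants' orders, whereas the last places in a known fixed block can be, so printing the block size in the protocol would give up that protection. If such a list already exists, say so at this place.

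The cost is preparing and concealing the list. Slight imbalance remains because 20 is not a multiple of six (two orders get one extra person), and dropout erodes some of the gain. No extra participants or visits are needed.

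### For participants taking analgesics, the required stop at least 24 hours before study entry can only happen before consent is signed

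*Protocol*

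**What the plan says.** The analgesic rule is in the protocol's Inclusion Criteria: "All analgesic medications will be discontinued at least 24 hours before entering the study and not be used until study participation is completed".

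The time of consent is given twice. The Methods say: "In the initial session (i.e., Block 1, Session 1) subjects will 1) be consented". Enrollment and Consent separately has the consent summary and form reviewed, and the document signed, during the first visit. Before that visit it describes a phone screening questionnaire for everyone. For clinic recruits it adds a discussion of the study and a copy of the consent form and/or summary, with the qualifier that this is on request. It describes no earlier signature.

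The Methods number the rest of that first session. The PDDS is step 2, the NPQ step 4 and the VAS step 5. The last step is "8) undergo either sham tDCS, tDCS at 2 mA, or tDCS at 4 mA". On session length they say: "The duration of each session will be approximately one hour".

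The three scores carry entry limits in the Inclusion Criteria:
- PDDS: "moderate disability (Patient Determined Disease Steps (PDDS) core 2-6"
- NPQ: "patients need to score greater than 0 on the Neuropathic Pain Questionnaire (NPQ) to qualify for the study"
- VAS: at least 40 on a 0 to 100 scale at baseline.

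**The concern.** Stopping pain medication is a change in treatment that the study requires. If it has to be done a day before the visit at which consent is signed, people with chronic neuropathic pain make that change before agreeing in writing to take part. For people not recruited at the clinic, no copy of the consent form before the visit is described. Because the entry scores are taken after the signature in that same session, some people may stop their medication for the study and be told the same day that they do not qualify.

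What is at stake is the protection of participants; no bias in the results is alleged.

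**Working it through.** There is no stated figure to reproduce. The check is a timeline, with the signature at t = 0.

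**Inputs**
- Analgesic stop: at least 24 h before entry (Inclusion Criteria).
- Signature: step 1 of Block 1, Session 1 (Methods); first visit (Enrollment and Consent).
- Session length: about 60 min (Methods).
- First stimulation: step 8, the last listed (Methods).
- Stimulation length: 20 min in all three conditions. For the active blocks, "The participant will receive tDCS for 20 min at an intensity of 2 mA or 4 mA"; for sham, the current ramps up for 30 seconds, "after which the current will be set to 0 for the remainder of the 20 minutes".

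**Formula**

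Latest permitted stop = time of entry − 24 h.

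The latest start of stimulation after signing is session length − 20 min = 60 − 20 = 40 min. This assumes the signature comes right at the start of the session. If it comes later, the time from signature to stimulation is shorter and the stop falls further ahead of the signature.

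**Results by meaning of study entry**

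| Entry means | Time of entry | Latest permitted stop, relative to signature |
|---|---|---|
| Signing consent | 0 | −24 h |
| Qualifying on PDDS, NPQ and VAS (between steps 1 and 8) | 0 to +40 min | between −24 h and −23 h 20 min |
| Starting first stimulation | up to +40 min | 40 min − 24 h = −23 h 20 min |

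**Range if the first session overruns** (assumed lengths, entry = start of stimulation)
- 90 min: 90 − 20 = 70 min; 70 min − 24 h = −22 h 50 min.
- 120 min: 120 − 20 = 100 min; 100 min − 24 h = −22 h 20 min.

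For the stop to follow the signature, more than 24 h would have to pass between signing and entry. A single session cannot contain that interval, so no reading of study entry puts consent first for someone who is taking analgesics.

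**Same-day ineligibility**

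Steps 2, 4 and 5 all follow step 1, so three entry limits are tested after the signature and about a day after the stop. How often someone would fail one of them cannot be worked out from the protocol.

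**The case against.** The order of events is not in dispute. The case on the other side concerns how much weight it bears.

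- **People may be informed beforehand.** Clinic recruits have the study discussed with them and may receive the consent text, and everyone is phoned. The qualifier about requests can be read as applying to the summary only. This stands: for some people the stop may be explained and voluntary. It is still unsigned, because a discussion or a copy is not a signature.
- **The consent process is only partly visible.** Consent pages were removed from the text at hand, the phone questionnaire is not reproduced, and no section says who tells people to stop, or when. This stands as a limit on what can be known about the instruction. It does not move the signature, which two sections place at the first visit.
- **The harm is bounded.** The unsigned period is about a day at minimum, the pain is by definition drug-resistant, and anyone found ineligible is no longer under the ban. The period off analgesics after signing is far longer: three 5-day blocks with two gaps of at least 7 days make 15 + 14 = 29 days, and consent covers that period. This is fair as to size. Yet resistance does not exclude partial relief, and the rule would be pointless if nobody took analgesics.
- **Same-day failure may be uncommon.** The PDDS could be asked by phone, and stopping analgesics should not lower a VAS score. This stands: such failure is possible, at an unknown rate, and the main point does not depend on it.
- **Minutes add little.** Agreed. The finding is about a day; the figures only show that it does not turn on one definition of entry.
- **Enrolment may be over.** The protocol's closing line, which calls this a case report without statistical analysis, may mean so, but it is ambiguous and does not change what the text requires.

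**Conclusion.** The concern holds. Two stated rules conflict: analgesics stop at least 24 h before entry, and consent is signed in the session that contains every plausible point of entry. For anyone taking analgesics, the stop precedes the signature by at least 24 h (entry = signing) or at least about 23 h 20 min (entry = first stimulation). The second figure falls only to about 22 h 20 min if the session is assumed to last two hours.

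The conclusion rests on the protocol's session order and its 24-hour rule, and on applying only to people who are taking analgesics. Neither their number nor the number who would stop and then prove ineligible is given. Confidence in the order of events is high; the extent of actual harm is unknown. The point should be corrected before anyone is asked to stop medication.

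A minor related mismatch: the analgesic ban has no exception, while Risks for subjects names non-prescription medication as what should relieve a headache, which it expects to be very rare.

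**What to change.** Obtain signed consent at the clinic, remotely or at another contact before any study-directed stop, and schedule Block 1, Session 1 at least 24 hours after the stop. Revise the Methods and Enrollment and Consent to match. Add to the Inclusion Criteria that nobody is to stop an analgesic for the study before signing. Someone may still fail a Session 1 score after stopping, but the stop will then have been consented to.

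Separately, make the Inclusion Criteria and Risks for subjects agree on headache medication, either by allowing an exception or by removing the suggestion.

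The cost is one earlier consent contact per person, including some later found ineligible, and a wording amendment. No study procedure has to be added.
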